6.4.10 Day 84 (Visit 10) ± 3 Days

The following procedures will be performed at Visit 10:

- Perform physical examination;
- Record weight;
- Calculate body mass index;
- Obtain vital signs including pulse rate, respiratory rate, and oral temperature;
- Obtain blood pressure;
 - O Blood pressures are to be obtained according to the AHA recommendations for accurate blood pressure measurement. Patients should avoid smoking, caffeine, or exercise within 30 minutes before measurement; empty his or her bladder; then sit quietly in a comfortable chair with back support for at least 10 minutes before measurement and remain still during the measurement. The patient's limb should be supported to measure blood pressure to ensure that the blood pressure cuff is at heart level, using the correct cuff size. Do not take the measurement over clothes. Blood pressure measurements should be performed in the

same arm throughout the study. Triplicate blood pressure measurements should be taken approximately 2 minutes apart with a validated, oscillometric upper arm blood pressure monitor. Trough cuff SBP and DBP values will be assessed based on the pre-defined blood pressure measurement guideline throughout the study. Pulse will be obtained simultaneously with blood pressure measurements;

- Obtain blood sample for clinical laboratory tests (central laboratory; see Appendix B);
- Obtain urine sample for:
 - o Urinalysis (central laboratory; see Appendix B);
 - o UACR; and
 - o 24-hour urine for UACR;
- Obtain serum sample for aldosterone;
- Obtain plasma sample for renin;
- Obtain serum sample for potassium (local and central laboratories);
- Obtain serum sample for creatinine (central laboratory);
- Obtain serum/plasma samples that will be stored at the central laboratory for determination of various additional biomarkers, including but not limited to galectin-3, NT-proBNP, IL-6, collagen biomarkers and CRP. The panel of biomarkers and time points for analysis will be determined prior to the database lock;
- Record adverse events and concomitant medications;
- Check study drug accountability and collect unused study drug; and
- Download 24-hour ABPM readings at site (for a subset of up to 40 patients per treatment group who agree to participate in 24-hour ABPM and still meet eligibility criteria at the end of the run-in period [Visit 3] who undergo 24-hour ABPM).

6.5 Day 112 (Visit 11) End of Study (Safety Follow-Up) ±5 Days

The following procedures will be performed at the End of Study (Safety Follow-Up) Visit (Visit 11):

- Record weight;
- Perform physical examination;
- Perform 12-lead ECG in triplicate (patients should be resting in a supine position for at least 10 minutes prior to assessment);
- Obtain vital signs including pulse rate, respiratory rate, and oral temperature;
- Obtain blood pressure;
 - O Blood pressures are to be obtained according to the AHA recommendations for accurate blood pressure measurement. Patients should avoid smoking, caffeine, or exercise within 30 minutes before measurement; empty his or her bladder; then sit quietly in a comfortable chair with back support for at least 10 minutes before measurement and remain still during

the measurement. The patient's limb should be supported to measure blood pressure to ensure that the blood pressure cuff is at heart level, using the correct cuff size. Do not take the measurement over clothes. Blood pressure measurements should be performed in the same arm throughout the study. Triplicate blood pressure measurements should be taken approximately 2 minutes apart with a validated, oscillometric upper arm blood pressure monitor. Trough cuff SBP and DBP values will be assessed based on the pre-defined blood pressure measurement guideline throughout the study. Pulse will be obtained simultaneously with blood pressure measurements;

- Obtain blood sample for clinical laboratory tests (central laboratory; see Appendix B);
- Obtain urine sample for:
 - o Urinalysis (central laboratory; see Appendix B); and
 - o UACR;
- Obtain plasma sample for PK from all patients;
- Obtain serum sample for pregnancy test (WOCBP only);
- Obtain serum sample for potassium (local and central laboratories);
- Obtain serum sample for creatinine (central laboratory); and
- Record adverse events and concomitant medications.

6.6 Early Termination Visit and Withdrawal Procedures

For patients who are withdrawn from the study prior to completion, the following procedures will be performed at an Early Termination Visit (as early as feasible after discontinuation of the study drug):

- Perform physical examination;
- Record weight;
- Contact IRT;
- Perform 12-lead ECG in triplicate (patients should be resting in a supine position for at least 10 minutes prior to assessment);
- Obtain vital signs including pulse rate, respiratory rate, and oral temperature;
- Obtain blood pressure;
 - O Blood pressures are to be obtained according to the AHA recommendations for accurate blood pressure measurement. Patients should avoid smoking, caffeine, or exercise within 30 minutes before measurement; empty his or her bladder; then sit quietly in a comfortable chair with back support for at least 10 minutes before measurement and remain still during the measurement. The patient's limb should be supported to measure blood pressure to ensure that the blood pressure cuff is at heart level, using the correct cuff size. Do not take the measurement over clothes. Blood pressure measurements should be performed in the same arm throughout the study. Triplicate blood pressure measurements should be taken approximately 2 minutes apart with a validated, oscillometric upper arm blood pressure

monitor. Trough cuff SBP and DBP values will be assessed based on the pre-defined blood pressure measurement guideline throughout the study. Pulse will be obtained simultaneously with blood pressure measurements;

- Obtain blood sample for clinical laboratory tests (central laboratory; see Appendix B);
- Obtain urine sample for:
 - o Urinalysis (central laboratory; see Appendix B); and
 - o UACR:
- Obtain plasma sample for PK from all patients;
- Obtain serum sample for aldosterone;
- Obtain plasma sample for renin;
- Obtain serum/plasma samples that will be stored at the central laboratory for determination of various additional biomarkers, including but not limited to galectin-3, NT-proBNP, IL-6, collagen biomarkers, and CRP. The panel of biomarkers and time points for analysis will be determined prior to the database lock;
- Obtain serum sample for pregnancy test (WOCBP only);
- Obtain serum sample for potassium (local and central laboratories);
- Obtain serum sample for creatinine (central laboratory);
- Record adverse events and concomitant medications;
- Check study drug accountability and collect unused study drug; and
- Download 24-hour ABPM readings at site if a patient has completed the 24-hour ABPM recording since their last visit (for a subset of up to 40 patients per treatment group who agree to participate in 24-hour ABPM and still meet eligibility criteria at the end of the run-in period [Visit 3] who undergo 24-hour ABPM).

7 EFFICACY ASSESSMENTS

7.1 Primary Efficacy Assessment

The primary efficacy variable is the change in trough-cuff resting seated SBP from baseline to Day 84.

Blood pressure must be measured in triplicate prior to study drug administration at the visits indicated on the Schedule of Procedures (Appendix A). Trough-cuff SBP values will be assessed based on the pre-defined blood pressure measure guideline throughout the study.

7.2 Secondary Efficacy Assessments

Twenty-four-hour ABPM monitoring will be assessed at the visits indicated on the Schedule of Procedures (Appendix A) in a subset of up to 40 patients per treatment group. At the end of the run-in period (Visit 3), ABPM will only be assessed for those patients who agree to participate in 24-hour ABPM and still meet all of the eligibility criteria. Blood pressure and HR measurements will be obtained every 20 minutes during the interval of 06:00:00 hours to 21:59:59 hours (to coincide with the daytime, awake period) and every 30 minutes during the interval of 22:00:00 hours to 05:59:59 hours (to coincide with the nighttime, sleeping period).

During the 24-hour ABPM recording period, a diary will be provided to the patient. Instructions and training will be provided to the site staff, who will in turn provide instructions to the patient.

The key secondary efficacy variables include the following:

• Change in trough-cuff seated DBP from baseline to Day 84;

Note: Blood pressure must be measured in triplicate prior to study drug administration at the visits indicated on the Schedule of Procedures (Appendix A). Trough-cuff DBP values will be assessed based on the pre-defined blood pressure measure guideline throughout the study.

- Change in 24-hour mean, daytime mean, nighttime mean, morning mean, last 6 hours of the dosing interval mean, SBP, DBP, MAP, and HR from baseline to Day 84 as measured by 24-hour ABPM in a subset of up to 40 patients per treatment group; and
- Change and percent change in UACR from baseline to Day 84 (for patients with albuminuria [defined as UACR >300 mg/g] or microalbuminuria [defined as UACR in the range of 30 mg/g to 300 mg/g]).

7.3 Pharmacokinetic Assessment

Plasma samples for PK analyses will be collected from all patients at the visits indicated on the Schedule of Procedures (Appendix A).

7.4 Pharmacodynamic Assessment

The pharmacodynamic (PD) variable of this study is the change in levels of serum aldosterone and plasma renin from baseline to Day 84. Serum samples for aldosterone and plasma samples for renin will be collected at the visits indicated on the Schedule of Procedures (Appendix A).

Serum/plasma samples will be stored at the central laboratory for determination of various additional biomarkers, including but not limited to galectin-3, NT-proBNP, IL-6, collagen

biomarkers, and CRP. The panel of biomarkers and time points for analysis will be determined prior to the database lock.

8 SAFETY ASSESSMENTS

Safety variables will include adverse events, vital signs (pulse rate, respiratory rate, and oral temperature), clinical laboratory findings, 12-lead ECGs, and physical examination findings.

The following serum potassium/hyperkalemia-related parameters and renal function-related parameters will be collected and evaluated:

- Incidence of hyperkalemia (defined as serum potassium ≥ 5.6 mmol/L), incidence of severe hyperkalemia (defined as serum potassium ≥ 6.0 mmol/L), and incidence of patients with serum potassium > 5.0 mmol/L;
- Change in serum potassium level from baseline to Day 84; and
- Change in eGFR and creatinine levels > 30% throughout the study period.

8.1 Adverse Events

An adverse event is defined as any untoward medical occurrence in a clinical investigation patient administered a pharmaceutical product, which does not necessarily have a causal relationship with this treatment. An adverse event can therefore be any unfavorable and/or unintended sign (including an abnormal laboratory finding), symptom, or disease temporally associated with the use of an investigational medicinal product, whether or not related to the investigational medicinal product. All adverse events, including observed or volunteered problems, complaints, or symptoms, are to be recorded on the appropriate eCRF.

Adverse events, which include clinical laboratory test variables, will be monitored and documented from the time of informed consent until study participation is complete. Patients should be instructed to report any adverse event that they experience to the Investigator. Beginning with the Screening Visit, Investigators should make an assessment for adverse events at each visit and record the event on the appropriate adverse event eCRF.

Wherever possible, a specific disease or syndrome rather than individual associated signs and symptoms should be identified by the Investigator and recorded on the eCRF. However, if an observed or reported sign or symptom is not considered a component of a specific disease or syndrome by the Investigator, it should be recorded as a separate adverse event on the eCRF. Additionally, the condition that led to a medical or surgical procedure (eg, surgery, endoscopy, tooth extraction, or transfusion) should be recorded as an adverse event, not the procedure.

Any medical condition already present at Screening should not be reported as an adverse event unless the medical condition or signs or symptoms present at baseline changes in severity or seriousness at any time during the study. In this case, it should be reported as an adverse event.

Clinically significant abnormal laboratory or other examination (eg, ECG) findings that are detected during the study or are present at Screening and significantly worsen during the study should be reported as adverse events. The Investigator will exercise his or her medical and scientific judgment in deciding whether an abnormal laboratory finding or other abnormal assessment is clinically significant. Clinically significant abnormal laboratory values occurring during the clinical study will be followed until repeat tests return to normal, stabilize, or are no longer clinically significant. Any abnormal test that is determined to be an error does not require reporting as an adverse event.

8.1.1 Adverse (Drug) Reaction

All noxious and unintended responses to a medicinal product related to any dose should be considered an adverse drug reaction. "Responses" to a medicinal product means that a causal relationship between a medicinal product and an adverse event is at least a reasonable possibility, ie, the relationship cannot be ruled out.

8.1.2 Unexpected Adverse Drug Reaction

An unexpected adverse drug reaction is defined as an adverse reaction, the nature or severity of which is not consistent with the applicable product information. For KBP-5074, the reference safety information is included in Section 5.1.6 of the Investigator's Brochure⁷ currently in force. The reference safety information will be reviewed yearly, and the periodicity of the review will be harmonized with the reporting period of the Development Safety Update Report.

8.1.3 Assessment of Adverse Events by the Investigator

The Investigator will assess the severity (intensity) of each adverse event as mild, moderate, or severe, and will also categorize each adverse event as to its potential relationship to study drug using the categories of yes or no.

Assessment of Severity:

Mild – An event that is easily tolerated and generally not interfering with normal daily activities.

Moderate – An event that is sufficiently discomforting to interfere with normal daily activities.

Severe – An event that is incapacitating with inability to work or perform normal daily activities.

Causality Assessment:

The relationship of an adverse event to the administration of the study drug is to be assessed according to the following definitions:

No (unrelated, not related, no relation) – The time course between the administration of study drug and the occurrence or worsening of the adverse event rules out a causal relationship and another cause (concomitant drugs, therapies, complications, etc.) is suspected.

Yes (related) – The time course between the administration of study drug and the occurrence or worsening of the adverse event is consistent with a causal relationship and no other cause (concomitant drugs, therapies, complications, etc.) can be identified.

The definition implies a reasonable possibility of a causal relationship between the event and the study drug. This means that there are facts (evidence) or arguments to suggest a causal relationship.

The following factors should also be considered:

- The temporal sequence from study drug administration-
 - The event should occur after the study drug is given. The length of time from study drug exposure to event should be evaluated in the clinical context of the event.
- Underlying, concomitant, intercurrent diseases-
 - Each report should be evaluated in the context of the natural history and course of the disease being treated and any other disease the patient may have.

Concomitant drug-

- The other drugs the patient is taking or the treatment the patient receives should be examined to determine whether any of them might be recognized to cause the event in question.
- Known response pattern for this class of study drug-
 - Clinical and/or preclinical data may indicate whether a particular response is likely to be a class effect.
- Exposure to physical and/or mental stresses-
 - The exposure to stress might induce adverse changes in the recipient and provide a logical and better explanation for the event.
- The pharmacology and PK of the study drug-
 - The known pharmacologic properties (absorption, distribution, metabolism, and excretion) of the study drug should be considered.

8.2 Adverse Events of Special Interest

The following adverse events of special interest must be reported to the Sponsor within 24 hours of the Investigator's awareness, even if not meeting the definition of an SAE:

- Hyperkalemia;
 - Mild hyperkalemia defined as serum potassium 5.0 mmol/L to 5.5 mmol/L (central or local laboratory);
 - o Moderate hyperkalemia defined as serum potassium 5.6 mmol/L to 5.9 mmol/L (central or local laboratory); and
 - o Severe hyperkalemia defined as serum potassium $\geq 6.0 \text{ mmol/L}$;
- Reduction from Day 1 eGFR levels \geq 30% throughout the duration of the study;
- Hypertensive emergency;
 - Defined as confirmed (based on the mean of at least 2 current consecutive protocol-required blood pressure readings, or otherwise obtained blood pressure readings) with SBP > 180 mmHg and/or DBP > 120 mmHg with associated new or progressive target organ damage, neurologic, and/or cardiac symptoms. Blood pressures of > 200 mmHg in asymptomatic patients should be recorded in the eCRF, and Investigators must differentiate between hypertensive urgency (markedly elevated blood pressure) and emergency. See Section 8.14 and Appendix C for definition and management of hypertensive emergencies and urgencies; and
- Symptomatic hypotension, or if the SBP < 90 mmHg after the first dose of study drug at Day 1.

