6.4.6 Day 40 (ABPM Visit) ± 3 Days

This visit is for 24-hour ABPM patients only (a subset of up to 40 patients per treatment group who agree to participate in 24-hour ABPM and still meet eligibility criteria at the end of the run-in period [Visit 3]).

The following procedure will be performed at the ABPM Visit:

• 24-hour ABPM device placement and start. Blood pressure and HR measurements will be obtained every 20 minutes during the interval of 06:00:00 hours to 21:59:59 hours (to coincide with the daytime, awake period) and every 30 minutes during the interval of 22:00:00 hours to 05:59:59 hours (to coincide with the nighttime, sleeping period). During the 24-hour ABPM recording period, a diary will be provided to the patient. Instructions and training will be provided to the site staff, who will in turn provide instructions to the patient.

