Symptomatic hypotension or a confirmed trough-seated SBP < 90 mmHg based on the mean of at least 2 current consecutive protocol-required blood pressure readings, or otherwise obtained blood pressure reading) after the first dose of study drug at Day 1, should be reported as an adverse event of special interest. Investigators should evaluate and correct any potential reasons that may contribute to hypotension, such as dehydration, decreased blood volume, potential overdose of

antihypertensive medication (including study drugs), etc. If symptomatic hypotension or a confirmed trough-seated SBP < 90 mmHg occurs, Investigators may consider down-titration of antihypertensive medications (other than study drug) first. If symptomatic hypotension or a confirmed trough-seated SBP < 90 mmHg persists following down titration study drug should be permanently discontinued.

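### Sections 8.2 and 8.14 define the hypotension adverse event of special interest differently, and neither says whether ambulatory readings count

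*Combined protocol and SAP*

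**What the plan says.** Section 8.2 lists the AESIs that a site must send to the sponsor within 24 hours of becoming aware of them. Its hypotension entry reads "Symptomatic hypotension, or if the SBP < 90 mmHg after the first dose of study drug at Day 1". Nothing is said about repeat measurement, posture, time since dose or the source of the reading.

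Section 8.14 covers the same event: "Symptomatic hypotension or a confirmed trough-seated SBP < 90 mmHg based on the mean of at least 2 current consecutive protocol-required blood pressure readings", then "or otherwise obtained blood pressure reading) after the first dose of study drug at Day 1". The bracket that closes there has no opening partner. The sentence ends with the reporting duty: the event "should be reported as an adverse event of special interest".

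The hypertensive emergency entry in Section 8.2 does state a confirmation rule: "Defined as confirmed (based on the mean of at least 2 current consecutive protocol-required blood pressure readings, or otherwise obtained blood pressure readings". It also sends the reader to Section 8.14 and Appendix C, but only for hypertensive emergencies and urgencies.

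Clinic blood pressure is taken in triplicate (Sections 6.2 to 6.6 and 8.8). Up to 40 patients per group also have 24-hour ambulatory monitoring on Days -1, 40 and 82 (Section 3.1). By day, "Blood pressure and HR measurements will be obtained every 20 minutes during the interval of 06:00:00 hours to 21:59:59 hours" (Section 7.2); by night, "every 30 minutes during the interval of 22:00:00 hours to 05:59:59 hours" (Section 6.4.6).

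Section 9.2.3 plans treatment-emergent adverse events by system organ class and preferred term, serious and related events, and summaries of laboratory values, vital signs, weight and physical findings. Sections 8 and 8.8 list vital signs as pulse, respiratory rate and temperature.

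**The concern.** Both sections govern reporting; they are not a reporting rule in one place and a separate management rule in the other. A site that works from the AESI list has no textual reason to confirm a low value or to limit itself to seated trough readings. A site that works from Section 8.14 has such a reason, but cannot tell what the alternative for readings from other sources admits.

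At stake is consistent ascertainment of hypotension across about 90 sites in a trial of a blood-pressure-lowering drug. Section 9.2.3 plans no count of low systolic values and Section 8 does not list blood pressure among the safety vital signs, so the planned safety evidence on hypotension rests on what investigators report. Those reports also feed the four-weekly blinded adverse event summary in Section 9.2.6.

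**Working it through.** The plan gives no figure to reproduce. The check compares the two texts, counts the scheduled ambulatory readings, and tests how far an assumed distribution can be relied on.

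**1. The two definitions side by side**

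| Element | Section 8.2 | Section 8.14 |
|---|---|---|
| Symptomatic hypotension | counts | counts |
| Threshold without symptoms | SBP < 90 mmHg | SBP < 90 mmHg |
| Starts | after first dose | after first dose |
| Confirmation | none stated | required; average of two or more successive scheduled readings |
| Posture and timing | none stated | seated, trough |
| Readings from other sources | not mentioned | mentioned; scope unclear |
| Ambulatory readings | not mentioned | not mentioned |

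The closing words of Section 8.14 can be read in two ways. On one, a single reading from another source is enough. On the other, the earlier requirement of a confirmed, seated trough value still governs it. The unmatched bracket leaves both open.

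**2. A clinic example (invented values)**

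Take a seated trough triplicate of 88, 93 and 95 mmHg in a patient without symptoms.
- Section 8.2: 88 < 90, so the literal text is met.
- Section 8.14, averaging rule: (88 + 93)/2 = 90.5; (93 + 95)/2 = 94; (88 + 93 + 95)/3 = 92. No average of successive readings is below 90, so the rule is not met.

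Section 8.14 also leaves open how many readings to average. With 88, 91 and 94 the first two give 89.5 and all three give 91, so the answer depends on that choice.

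**3. Scheduled ambulatory readings after the first dose**

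- Day: 16 h x 3 per hour = 48. Night: 8 h x 2 per hour = 16. Per session: 48 + 16 = 64.
- Post-dose sessions: Days 40 and 82, so 2 x 64 = 128 per patient.
- Patients: at most 3 x 40 = 120, so at most 120 x 128 = 15,360 readings.

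**4. How many patients would have one below 90 mmHg**

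The documents give no ambulatory mean or SD, so every input here is an assumption. Let a patient's deviation b be normal with mean 0 and the between-patient SD, and let readings be independent normal around the night mean N + b or the day mean D + b with reading SD s. Over two sessions there are 32 night and 96 day readings:

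P(at least one < 90) = 1 - E_b{ [1 - Φ((90 - N - b)/s)]^32 x [1 - Φ((90 - D - b)/s)]^96 }

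| Night / day mean (mmHg) | Between-patient SD | Reading SD | P | Of 120 |
|---|---|---|---|---|
| 140 / 148 | 10 | 8 | 0.1% | 0.1 |
| 145 / 150 | 12 | 10 | 0.6% | 0.7 |
| 140 / 148 | 13 | 10 | 2.1% | 2.5 |
| 135 / 145 | 15 | 12 | 11.8% | 14 |
| 130 / 140 | 15 | 12 | 19% | 23 |
| 130 / 140 | 15 | 14 | 28% | 34 |

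The answer moves from almost nobody to more than a quarter of the subset. It shows that the silence on ambulatory readings could matter; it does not forecast a count.

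**The case against.** The strongest defence is that Section 8.2 is a list and Section 8.14 supplies the detail, so a sensible site would read the two together. That is a fair expectation of conduct, but the text does not direct it: the cross-reference in Section 8.2 is confined to hypertensive emergencies and urgencies, and the neighbouring entry shows that the list does state confirmation where it is wanted.

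A reader might go further and infer that single ambulatory readings count under Section 8.2 and not under Section 8.14, so that they would dominate one count while the other stayed near zero. The documents do not support this. Section 8.2 never mentions ambulatory readings. The alternative in Section 8.14 may admit a single reading from another source, and both sections count symptomatic events. Ambulatory monitoring is placed among the efficacy assessments in Section 7.2, and no section tells sites to screen individual readings for AESIs. The 24-hour duty runs from the investigator's awareness, so a reading below 90 mmHg is not automatically a report.

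Nor can the hypotension AESI be called a main safety output. Section 9.2.3 plans no by-arm table of it, and the parameters that Section 8 singles out are potassium and renal function. Finally, the design is double-blind with up to 40 ambulatory patients in each arm, so nothing shows that inconsistent reporting would favour an arm. These limits stand. They narrow the point without removing the conflict between the sections.

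**Conclusion.** The conflict is in the current text: the two sections differ on confirmation, posture and timing for the same reportable event, Section 8.14 is unclear about readings from other sources, and neither deals with ambulatory readings. The consequence is inconsistent hypotension reporting between sites. This is a minor point. It leaves the primary analysis of systolic change untouched, and no between-arm bias is shown.

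The wording conflict rests on no assumption. Its numerical effect cannot be fixed from the documents: the 0.1% to 28% range depends wholly on assumed means and SDs and on independent normal readings.

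**What to change.** Reconcile Sections 8.2 and 8.14 into one AESI definition, or have the hypotension entry in 8.2 refer expressly to 8.14. The agreed text should settle:

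- whether confirmation is required, and how many readings are averaged;
- posture and time since dose;
- what the alternative for readings from other sources admits, with the bracket repaired;
- whether ambulatory readings count.

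Which rule is right is for the sponsor and its clinicians; this review proposes none.

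In Section 9.2.3, add a by-arm count and percentage of Safety Population patients with at least one post-dose seated triplicate mean SBP below 90 mmHg, and state which visits are included. This uses clinic readings already collected and does not depend on how a site read the AESI rule.

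Cost: one sentence and one derived table row. No new data or visits are needed, and the sample size does not change.
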